12.0 MEASUREMENT OF EFFECT

Response criteria will be defined by the IWG criteria ET 2006. Patients will be assessed for response at the end of induction cycle.

Response criteria will be defined as follow:

Response	Definition Responses must be for at least 4 weeks)
Complete remission (CR)	Marrow: < 5% myeloblasts with normal maturation of all cell lines. Persistent dysplasia will be noted (dysplastic changes should consider the normal range of dysplastic changes.) Blood: 
- Hemoglobin (Hgb) \geq 11 g/dL (untransfused, patient not on EPO)- Neutrophils \geq 1x10⁹/L (not on myeloid growth factor)- Platelets \geq 100 x 10⁹/L (not on thrombopoietic agent)- No blasts
Partial remission (PR)	All CR criteria (if abnormal prior to treatment), except: Marrow blasts decreased by \geq 50% compared with pretreatment but still $>$ 5%. Cellularity and morphology not relevant
Marrow CR	Marrow: \leq 5% myeloblasts and decrease by \geq 50% over pretreatment Blood: if hematologic improvement (HI) responses, they will be noted in addition to the marrow CR
Stable disease (SD)	Failure to achieve at least PR, but no evidence of progression for $>$ 8 weeks
Failure	Death during treatment or disease progression characterized by worsening of cytopenias, increase in percentage of marrow blasts, or progression to an MDS FAB subtype more advanced than pretreatment.

Relapse after CR or PR (PD)	
At least one of the following:
 
 - Return to pretreatment bone marrow blast percentage - Decrement of $\geq 50\%$ from maximum remission/response levels in granulocytes or platelets - Reduction in Hgb concentration by ≥ 1.5 g/dL or transfusion dependence (in the absence of another explanation, such as acute infection, GI bleeding, hemolysis, etc.)
Cytogenetic response	
Complete: Disappearance of the chromosomal abnormality without appearance of new ones
 
Partial: At least 50% reduction of the chromosomal abnormality

Hematologic Improvement	Response Criteria (responses must last at least 8 weeks)
Erythroid response (pretreatment, < 11 g/dL)	
Hgb increase by ≥ 1 g/dL
 
Relevant reduction of units of RBC transfusions by an absolute number of at least 4 RBC transfusions/8wk compared with the pretreatment transfusion number in the previous 8 wk.
 
Only RBC transfusions given for a Hgb of ≤ 9 g/dL pretreatment will count in the RBC transfusion response evaluation

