Platelet response (pretreatment, $< 100 \times 10^9/L$)	
Absolute increase of $\geq 30 \times 10^9/L$ for patients starting with $> 20 \times 10^9/L$
 
Increase from $< 20 \times 10^9/L$ to $> 20 \times 10^9/L$ and by at least 100%

Neutrophil response (pretreatment, $< 1 \times 10^9/L$)	
At least 100% increase an absolute increase $> 0.5 \times 10^9/L$

Progression or relapse after HI	
At least 1 of the following:
 
At least 50% decrement from maximum response levels in granulocyte or platelets
 
Reduction in Hgb by ≥ 1.5 g/dL
 
Transfusion dependence (in the absence of another explanation, such as acute infection, GI bleeding, hemolysis, etc.)

Table 3: Response Criteria for MDS Patients

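### Table 3 scores erythroid improvement at a 1 g/dL hemoglobin rise but its loss only at a 1.5 g/dL fall, so a gain of 1.0 to under 1.5 g/dL can vanish without meeting the hemoglobin loss rule

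*Combined protocol and SAP*

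**What the plan says.** Section 12.0 names the IWG 2006 criteria as its source and writes them out in Table 3. The row headed "Erythroid response (pretreatment, < 11 g/dL") gives two routes to an erythroid response. One is a hemoglobin rise, "Hgb increase by ≥ 1 g/dL". The other is a drop of at least four red cell transfusions per 8 weeks. The HI block carries a duration condition: "Response Criteria (responses must last at least 8 weeks").

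The row for progression or relapse after HI can be met in any of three ways:
- on hemoglobin, by "Reduction in Hgb by ≥ 1.5 g/dL"
- on the other two lineages, by "At least 50% decrement from maximum response levels in granulocyte or platelets"
- by the patient coming to depend on transfusion when nothing else accounts for it.

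The granulocyte and platelet item names the level from which the fall is counted. The hemoglobin item does not.

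The row for relapse after CR or PR uses the same 1.5 g/dL hemoglobin fall. The CR row requires hemoglobin to be "untransfused, patient not on EPO"; the erythroid HI line has no such condition. Section 6.2 leaves erythropoietin to the treating physician's discretion during the study.

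**The concern.** A rule for losing a response would normally recognize that the gain has gone. Here the entry bar is 0.5 g/dL lower than the exit bar, and the HI loss row has no criterion for a return to pretreatment hemoglobin. The only return-to-pretreatment criterion in Table 3 concerns marrow blasts, in the relapse row for CR and PR.

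What is at stake is how HI is classified and how long it appears to last. Compared with a 1.5 g/dL bar, a 1 g/dL bar can only add patients to the HI group, and the higher exit bar can only keep them there longer. If HI were counted as a response, the same bias would pass into ORR, the primary endpoint, and into DOR, a secondary one. Section 14 rejects the null hypothesis at 4 or more responses in 18, so under that reading one patient could matter.

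**Working it through.** No sample size, power or error rate in the plan depends on these thresholds, so there is no design figure to reproduce. The check compares the two rules directly.

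**Inputs (all from Table 3).** Entry: a rise of at least 1.0 g/dL. Loss on hemoglobin: a fall of at least 1.5 g/dL. Assumption: the fall is counted from the maximum response level, as the table states for granulocytes and platelets.

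**Formula.** Let B be pretreatment hemoglobin and g the peak gain, held for 8 weeks. The peak is B + g. Loss is scored at B + g − 1.5, so the trigger relative to pretreatment is g − 1.5. A return to exactly B is a fall of g, which counts as loss only if g ≥ 1.5.

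| Peak gain g (g/dL) | Response? | Back at B: loss on hemoglobin? | Trigger relative to B, g − 1.5 |
|---|---|---|---|
| 0.9 | no | – | – |
| 1.0 | yes | no | −0.5 |
| 1.2 | yes | no | −0.3 |
| 1.4 | yes | no | −0.1 |
| 1.5 | yes | yes | 0.0 |
| 2.0 | yes | yes | +0.5 |

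**Example.** Hemoglobin rises from 8.0 to 9.0 and stays there 8 weeks: response. It then falls back to 8.0, a fall of 1.0, so there is no loss on hemoglobin. Loss is scored at 9.0 − 1.5 = 7.5.

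**Reference level.** If the fall were instead counted from pretreatment, the trigger would be B − 1.5 for every responder and the gap would be wider. The 0.5 g/dL maximum therefore belongs to the more favorable reading.

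**Equal thresholds.** With both at 1.5, every hemoglobin-route responder has g ≥ 1.5, so a return to B is a fall of at least 1.5 and counts as loss. With both at 1.0 the same holds, since g ≥ 1.0. Either value closes the gap for this route.

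**Which figure is the odd one.** The 1.5 g/dL figure stands in both relapse rows; the 1 g/dL figure stands only in the erythroid row. The neutrophil rule is coherent: entry needs at least a doubling, and a 50% fall from a doubled count lands at or above the starting count.

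**The case against.** The strongest reply is that separate entry and exit thresholds run through Table 3, so asymmetry alone does not prove an error. This is correct. A platelet count rising from 80 to 110 (× 10⁹/L) meets the response rule, yet a 50% fall from maximum is 55, well below 80. For a gain of exactly 30, this happens at any starting count above 30, because (b + 30)/2 < b when b > 30. Likewise, hemoglobin rising from 10.0 to 11.0 can satisfy the CR hemoglobin line, while the 1.5 g/dL relapse fall lands at 9.5.

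Several stronger readings are tempting, and the documents do not support them:

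- **Any erythroid responder back at pretreatment hemoglobin stays in response.** Gains of 1.5 g/dL or more meet the loss rule on return, and transfusion dependence or a 50% fall in granulocytes or platelets ends the response by another route.
- **Transfused rises simply count.** Transfusion dependence is itself a loss criterion, so a rise held up for 8 weeks by regular transfusion would ordinarily meet it. The missing EPO condition is the clearer gap. The platelet and neutrophil HI lines also lack the growth-factor conditions of the CR row, so the omission is not peculiar to hemoglobin.
- **ORR is inflated.** Section 6.1 opens consolidation to CR, CRi or PR only. Section 14 names CR and CRi and then breaks off, without naming HI. ORR is read at day 35 ± 10, so by day 45 at the latest, and an 8-week (56-day) improvement cannot be confirmed at that visit. Section 2 lists neither an HI rate nor an HI duration as an objective.
- **Eligibility is affected.** Inclusion criterion 4 uses HI by IWG 2006 but cites the publication, not Table 3.
- **Matching thresholds would keep the loss trigger from ever falling below pretreatment.** Responders by transfusion reduction need no hemoglobin rise, so for them a 1.5 g/dL fall can still end below pretreatment.

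The existence of the gap survives: no other section closes it for gains of 1.0 to under 1.5 g/dL.

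**Conclusion.** The point holds in a narrow form. An erythroid responder by hemoglobin with a peak gain of 1.0 to under 1.5 g/dL can lose the whole gain and still be scored as in response, with the trigger 0.1 to 0.5 g/dL below pretreatment for gains of 1.4 down to 1.0. This rests on the gain having lasted 8 weeks, on the fall being counted from the maximum response level, and on neither of the other loss routes applying.

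The direct effect is on HI as noted under Table 3. An effect on ORR or DOR is conditional on HI being counted as a response, which Section 14 leaves open. The documents do not give the frequency of such gains, so the number of patients affected cannot be estimated. The internal evidence favors 1.5 g/dL, but the cited criteria are not reproduced, so the intended value cannot be settled from the documents alone. This is a minor correction to an operative response definition, worth making because it costs almost nothing.

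**What to change.** In Table 3:

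1. Reconcile the erythroid HI entry threshold with the HI loss threshold, and check both against the IWG 2006 criteria that Section 12.0 names. The table's relapse rows point to 1.5 g/dL for both; adopt it only after that check.
2. State that the hemoglobin fall is measured from the maximum response level, as the table already does for granulocytes and platelets.
3. State that the rise is judged on hemoglobin not supported by transfusion or EPO, in line with the CR row, if the cited criteria allow it.

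The change is one number and a few words, with no new data collection. If 1.5 g/dL is adopted, slightly fewer patients will be scored as erythroid HI.

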13.0 DATA REPORTING / REGULATORY CONSIDERATIONS

Adverse event lists, guidelines, and instructions for AE reporting can be found in Section 8.0 (Adverse Events: List and Reporting Requirements).

13.1 Data Reporting

The OnCore® Database will be utilized, as required by the Case Comprehensive Cancer Center, to provide data collection for both accrual entry and trial data management. OnCore® is a Clinical Trials Management System housed on secure servers maintained at Case Western Reserve University. OnCore® Access to data through OnCore® is restricted by user accounts and assigned roles. Once logged into the OnCore® system with a user ID and password, OnCore® defines roles for each user which limits access to appropriate data. User information and password can be obtained by contacting the OnCore® Administrator at [contact].

OnCore® is designed with the capability for study setup, activation, tracking, reporting, data monitoring and review, and eligibility verification. This study will utilize electronic Case Report Form completion in the OnCore® database. A calendar of events and required forms are available in OnCore®.

13.2 Regulatory Considerations

The study will be conducted in compliance with ICH guidelines and with all applicable federal (including 21 CFR parts 56 & 50), state or local laws.

13.2.1 Written Informed consent

Provision of written informed consent must be obtained prior to any study-related procedures. The Principal Investigator will ensure that the subject is given full and adequate oral and written information about the nature, purpose, possible risks and benefits of the study as well as the subject's financial responsibility. Subjects must also be notified that they are free to discontinue from the study at any time. The subject

should be given the opportunity to ask questions and be allowed time to consider the information provided.

The original, signed written Informed Consent Form must be kept with the Research Chart in conformance with the institution's standard operating procedures. A copy of the signed written Informed Consent Form must be given to the subject. Additionally, documentation of the consenting process should be located in the research chart.

13.2.2 Subject Data Protection

In accordance with the Health Information Portability and Accountability Act (HIPAA), a subject must sign an authorization to release medical information to the sponsor and/or allow the sponsor, a regulatory authority, or Institutional Review Board access to subject's medical information that includes all hospital records relevant to the study, including subjects' medical history.

13.2.3 Retention of records

The Principal Investigator of The Case Comprehensive Cancer Center supervises the retention of all documentation of adverse events, records of study drug receipt and dispensation, and all IRB correspondence for as long as needed to comply with local, national and international regulations. No records will be destroyed until the Principal Investigator confirms destruction is permitted.

13.2.4 Audits and inspections

Authorized representatives of the sponsor, a regulatory authority, an Independent Ethics Committee (IEC) or an Institutional Review Board (IRB) may visit the site to perform audits or inspections, including source data verification. The purpose of an audit or inspection is to systematically and independently examine all study-related activities and documents to determine whether these activities were conducted, and data were recorded, analysed, and accurately reported according to the protocol, Good Clinical Practice (GCP), guidelines of the International Conference on Harmonization (ICH), and

any applicable regulatory requirements. For multi-center studies, participating sites must inform the sponsor-investigator of pending audits.

14.0 STATISTICAL CONSIDERATIONS

In determining the sample size for the patient cohort, Minimax Simon's two-stage design (Simon, 1989) will be used. The null hypothesis that the true response rate is 0.1 will be tested against a one sided alternative. In the first stage, 7 patients will be accrued in each arm. If there are two or less responses in these 7 patients, the arm will be stopped. Interim analysis will be conducted to determine the benefit of applying the drug in each arm. In the winning arm, 11 additional patients will be accrued for a total of 18. The null hypothesis will be rejected if 4 or more responses are observed in 18 patients. This design yields a type I error rate of 0.1 and power of 0.8 when the true response rate is 0.3.

Descriptive statistical analysis will be calculated, including histograms or box-plots, proportions, range, means and standard deviations. Fisher's exact test and Wilcoxon rank test will be used in univariate analyses of categorical and continuous variables, respectively. Overall response (CR + CRI +) rate and its 95% CI. Given there is no adjustment for multiple comparisons, need to note the p-values from the univariate analyses will be nominal and not used to infer significance.

Toxicity Monitoring Rules

The following toxicity monitoring plan will terminate the trial early given evidence for excessive rates of toxicity with CPX-351 based on the method of Thall et al.¹⁴ Early termination will be applied to evaluate patients experiencing toxicity defined as any grade ≥ 3 non-hematologic AE that is determined to be at least possibly related to CPX-351. A total of 25 patients will be enrolled. The monitoring rules target a toxicity rate of 20% and assume a non-informative Beta (0.2, 0.8) prior distribution. The trial will stop early for toxicity if $\text{Pr}(\text{Toxicity Rate} > 0.20 | \text{data}) > 0.85$, i.e. stop early if the evidence for excessive toxicity (higher than 20%) for the target population given observed data is sufficiently high (probability > 0.85). Monitoring will be carried out

from the 3rd patient. Table 5 summarizes the resultant stopping boundaries and Table 6 summarizes the trial's operating characteristics.

Table 5. Summary of early stopping boundaries from the 3rd patient. Target toxicity rate is 20%. Using prior of Beta (0.2, 0.8) and posterior probability threshold of 0.85. E.g. If 3 or more patients experience grade ≥ 3 non-hematologic AEs out of the first 6 patients, the trial will stop early. Whenever a grade ≥ 3 non-hematologic AE is observed, check this table to see if the boundary has been crossed. E.g. if a total of 4 grade ≥ 3 non-hematologic AEs has been observed on trial, and the total number of patients treated is 9 or less, then stop the trial for excessive toxicity.

Stop Early if #Patients Experienced grade ≥ 3 non-hematologic AE	2	3	4	5	5	6	7	8
Total #Patients Treated	3	6	9	12	15	18	21	24

Table 6. Summary of operating characteristics based on 10,000 simulations using boundaries in Table 5 for early stopping. For example, if the true toxicity rate is 20%, the probability of early stopping is 0.27, and if the true toxicity rate is 40%, the probability of early stopping is 0.88.

Scenario	True Toxicity Rate	Pr(Early Stop)	Average #Patients Treated	Average #Toxicities
1	- 0.10	0.05	23.2	2.3
2	0.20	0.27	19.8	4.0
3	0.30	0.62	14.6	4.4
4	0.40	0.88	9.8	3.9

Summary statistics of toxicity will be provided in frequencies and percentages. Toxicity rate will be estimated along with 95% CIs. Other statistical analyses will be carried out as appropriate.

REFERENCES

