6.0 Treatment Plan

6.1 Treatment Regimen Overview Consent and Screening

Upon signing consent, patients will begin the screening phase. The screening period begins the day the patient signs consent and can take place over a 28 day period leading up to dosing on day 1 (D1). During the screening period patients will be assessed to determine if they meet eligibility for this study per the inclusion and exclusion criteria as outlined in sections 4.1 and 4.2. Once the patient is deemed eligible they will be stratified into two arms based on the post-HMA failure model (Appendix V).

Stratification

Prior to beginning treatment, all eligible patients will be stratified into low vs. high risk based on the post-HMA failure model (Appendix V)⁴. Seven patients will be enrolled into the low risk arm and seven patients will be enrolled into the high risk arm. Once 14 patients, across both arms, have been enrolled and evaluated for a response (D35 +/- 10 days bone marrow), an interim analysis will be conducted to determine benefit in

each arm. The arm with the greatest response will then enroll an additional 11 patients, for a total of 18 patients in that arm. Overall, this study will enroll 25 patients.

Induction

The induction phase is defined as the time between the first day (D1) of study drug to day 35 and/or count recovery. During the induction phase of the study, all patients will be treated with the FDA approved standard dose of CPX-351 at 44mg/m² (daunorubicin 44 mg/m² and cytarabine 100 mg/m²) on days 1, 3, and 5. Study drug will be administered per the study calendar (section 11.2) unless patient exhibits any EOT criteria. Premedication with anti-emetics is recommended prior to treatment with CPX-351. No re-induction will be allowed and no day 14 bone marrow biopsy is required. A bone marrow biopsy and aspirate will be obtained on day 35 +/-10 days to confirm response. If no evidence of blasts > 5%, G-CSF will be allowed to improve counts at the discretion of the treating physician. Following the bone marrow, patients who meet the response criteria per section 12.0 can then continue onto the consolidation phase of this study.

Consolidation

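### The stage-1 stopping rule (2 or fewer responses in 7) does not belong to the stated Simon design: it cuts per-arm power from 0.80 to 0.35 and conflicts with Section 6.1

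*Combined protocol and SAP*

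**What the plan says.** Section 14.0 names the design ("Minimax Simon's two-stage design (Simon, 1989) will be used") and the hypothesis ("The null hypothesis that the true response rate is 0.1 will be tested against a one sided alternative"). Stage 1 is set by "In the first stage, 7 patients will be accrued in each arm", and the futility rule follows: "If there are two or less responses in these 7 patients, the arm will be stopped". For stage 2, "In the winning arm, 11 additional patients will be accrued for a total of 18". The null is rejected at 4 or more responses in 18. The section then claims: "This design yields a type I error rate of 0.1 and power of 0.8 when the true response rate is 0.3".

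Section 6.1 (Stratification) describes the same 7 + 7 + 11 structure, where the two arms are the low-risk and high-risk groups of the post-HMA failure model. It gives no numerical futility boundary. After an interim look at 14 patients, "The arm with the greatest response will then enroll an additional 11 patients, for a total of 18 patients in that arm", and "Overall, this study will enroll 25 patients".

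**The concern.** An arm must have at least 3 responses in 7 patients (43%) to continue, in a design meant to detect a true rate of 30%. An arm at the target rate expects 7 × 0.3 = 2.1 responses in stage 1, so the rule closes an arm that performs as hoped. The claimed power of 0.8 is then out of reach.

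This rule governs the primary endpoint at the only planned efficacy decision before the final test. If the team follows Section 14.0, it will probably abandon an arm at the target rate. If it follows Section 6.1, it overrides the futility rule. When the two sections disagree, the choice between them would be made after the stage-1 responses are known.

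**Working it through.** **Inputs, all from Section 14.0.** p0 = 0.1; p1 = 0.3; n1 = 7 per arm; 11 more in stage 2, so n = 18; reject at 4 or more responses (r = 3); stop at r1 = 2 or fewer in stage 1.

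**Formula, one arm alone.** With b(x; 7, p) the binomial probability of x responses in 7, and X2 ~ Bin(11, p):

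P(reject) = Σ over x1 > r1 of b(x1; 7, p) × P(X2 ≥ 4 − x1)

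The terms are:

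| Stage-1 responses x1 | b at 0.1 | P(X2 ≥ 4 − x1) at 0.1 | Product | b at 0.3 | P(X2 ≥ 4 − x1) at 0.3 | Product |
|---|---|---|---|---|---|---|
| 1 | 0.3720 | 0.0896 | 0.0333 | 0.2471 | 0.6873 | 0.1698 |
| 2 | 0.1240 | 0.3026 | 0.0375 | 0.3177 | 0.8870 | 0.2818 |
| 3 | 0.0230 | 0.6862 | 0.0158 | 0.2269 | 0.9802 | 0.2224 |
| 4 to 7 | 0.0027 | 1 | 0.0027 | 0.1260 | 1 | 0.1260 |

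**Reproducing the stated figures.** Summing from the first stage-1 count that continues:

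| Stop an arm at | Type I error (p = 0.1) | Power (p = 0.3) | P(stop at stage 1), p = 0.1 | P(stop at stage 1), p = 0.3 |
|---|---|---|---|---|
| no interim stop | 0.098 | 0.835 | 0 | 0 |
| 0 of 7 | 0.0893 | 0.8000 | 0.478 | 0.082 |
| 1 or fewer | 0.056 | 0.630 | 0.850 | 0.329 |
| 2 or fewer (Section 14.0) | 0.0185 | 0.348 | 0.974 | 0.647 |

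Of the rules that stop early, only 0 of 7 gives the stated power of 0.8 while keeping type I error within 0.1.

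**A different final cut-off cannot repair it.** Reaching stage 2 requires 3 or more of 7, with probability 0.2269 + 0.1260 = 0.353 at p = 0.3. Power cannot exceed 0.353 whatever the final criterion.

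**Which design was meant.** A search of all two-stage designs up to n = 30 with type I error ≤ 0.10 and power ≥ 0.80 gives a minimum n of 18. Among designs of that size, the smallest expected sample size under p0 (12.7) belongs to n1 = 7, r1 = 0, r = 3. That matches Section 14.0 in n1, n, final cut-off and power; only the stage-1 boundary differs. With n = 18 and r = 3, a boundary of r1 = 2 reaches power 0.80 only if n1 is 15 or more.

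**Both arms together, boundary of 2.** If both arms are at 0.3, both close at stage 1 with probability 0.647² = 0.419. Choosing the better arm does not rescue the rule. With ties broken at random (an assumption, as the documents give no tie rule), a 0.3 arm paired with a 0.1 arm is chosen and declared active with probability 0.345.

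**How often Sections 6.1 and 14.0 disagree.** They disagree when the better arm has 2 or fewer responses, which means that both arms do:

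- both at 0.3: 0.647 × 0.647 = 0.42
- one at 0.3, one at 0.1: 0.647 × 0.974 = 0.63
- both at 0.1: 0.974 × 0.974 = 0.95

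**The case against.** The arithmetic is not in dispute. Five points bear on how far the conclusion reaches.

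1. **Selecting a winner.** A boundary of 0 of 7 restores the stated figures only for one arm taken alone. Only the better arm goes on. With random tie-breaking, the chance of a false positive in either arm is 0.149 when both are at 0.1, and power for a 0.3 arm paired with a 0.1 arm is 0.715. This stands and should be reported, but it does not defend a boundary of 2.
2. **Whether the sections truly conflict.** Section 6.1 omits a futility stop and does not deny one. It describes the interim as a judgement of benefit in each arm, and Section 14.0 itself contains both a stop and a winning arm, so the two steps could be sequential. That is a fair reading, but Section 6.1 is worded unconditionally on both the 11 further patients and the total of 25, so it still needs reconciling.
3. **Direction of the error.** The rule is conservative on type I error (0.018 against 0.1). The harm is lost power and wrongly closed arms, not false claims of efficacy.
4. **Timing.** This is Version 5.0, dated 18 January 2021, and first enrolment was estimated for March 2019. The documents do not say whether the 14-patient interim has happened. If it has, moving the boundary is a change made after seeing data.
5. **Other mentions of 25.** The planned number also appears in the Protocol Summary, in Section 3.2 (as approximate) and in the toxicity monitoring text of Section 14.0, so the edit reaches beyond two sentences.

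**Conclusion.** The concern holds and must be fixed. With the boundary in Section 14.0, per-arm power is 0.35 instead of 0.80, type I error is 0.018 against a nominal 0.1, and an arm at the 30% target is closed after stage 1 about two times in three (0.647). Every other element matches the minimax design that stops at 0 of 7. Section 6.1 does not carry the stop, so the two sections give incompatible directions with probability 0.42 to 0.95 over the scenarios examined.

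The per-arm figures are exact and assume only independent responses with a common rate within an arm. The conflict probabilities also assume that the arms are independent and that Section 6.1 is taken at its word. The figures that include selection also assume random tie-breaking.

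**What to change.** **If the interim has not taken place:**

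- In Section 14.0, set the stage-1 boundary to 0 of 7, for example: *An arm with no response among its first 7 patients closes to accrual.* With n1 = 7, n = 18 and r = 3, this is the only cut that keeps a futility stop and meets the stated error rates.
- In Section 6.1, state the same boundary, require an arm to clear it before it can be chosen for expansion, and add a tie rule.
- Make the total a maximum of 25, and align the Protocol Summary, Section 3.2 and the toxicity monitoring text. If both arms stop, the trial ends at 14.
- Say that 0.089 and 0.800 are per-arm figures before selection, and report the figures with selection beside them (0.149 and 0.715 under random tie-breaking).

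**If the bar of 3 in 7 is intended,** keep it and restate the per-arm figures as type I error about 0.02 and power about 0.35. Section 6.1 still has to carry the stop.

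**If the interim has already taken place,** record which rule was applied and when, and report the operating characteristics of that rule. Any new boundary should be identified as a post-interim change.

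The cost is a few sentences in Sections 14.0 and 6.1 and consistent wording wherever 25 appears. No patients beyond the planned 25 are needed.

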3.2 Number of Subjects

Approximately 25 patients will be enrolled in this trial.

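### The type I error of 0.1 and power of 0.8 in section 14 do not belong to the design written there: one arm has 0.0185 and 0.348, and no figures cover expanding only the better of two strata

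*Combined protocol and SAP*

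**What the plan says.** Section 14.0 names a "Minimax Simon's two-stage design" for a null response rate of 0.1, tested one-sided. Each of two arms, the low-risk and high-risk strata of the post-HMA failure model, enrols 7 patients. The stage-1 rule is: "If there are two or less responses in these 7 patients, the arm will be stopped". Then: "In the winning arm, 11 additional patients will be accrued for a total of 18". The final rule is: "The null hypothesis will be rejected if 4 or more responses are observed in 18 patients". One pair of operating characteristics follows: "This design yields a type I error rate of 0.1 and power of 0.8 when the true response rate is 0.3".

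Section 6.1 (Stratification) describes the same interim analysis after 14 patients but repeats no stage-1 cut. It says: "The arm with the greatest response will then enroll an additional 11 patients, for a total of 18 patients in that arm", and then: "Overall, this study will enroll 25 patients". Section 3.2 puts it as: "Approximately 25 patients will be enrolled in this trial".

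Neither section gives a tie rule. Neither says whether the error rate is per stratum or for the trial, or whether the power assumes one or both strata at 0.3.

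**The concern.** There are two separate problems.

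- **The stage-1 cut.** Requiring at least 3 responses in 7 is severe when the rate of interest is 0.3, where the expected count is 7 × 0.3 = 2.1. An arm that truly responds at 0.3 would usually be stopped, so a power of 0.8 looks impossible.
- **The selection step.** A single-arm Simon design has one arm and one chance to reject. Here two strata compete for the second stage. Selection can raise the chance of some false rejection, and it can lower the chance that a truly active stratum is the one expanded. A single-arm pair of figures does not describe this.

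The rule decides the primary endpoint. A reader would take 0.1 and 0.8 as the trial's error rates. If the written cut is applied literally, the trial will more likely than not miss a drug that is active in one stratum.

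**Working it through.** **Inputs** (section 14.0, with the strata and selection also in section 6.1): n1 = 7 per arm; stop if responses ≤ r1 = 2; 11 more patients for n = 18; reject if the total is ≥ 4; p0 = 0.1; p1 = 0.3.

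**Step 1: one arm as written.** The rejection probability is the sum over x > r1 of P(X = x; 7, p) × P(Bin(11, p) ≥ 4 − x).

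| x of 7 | P(x), p = 0.1 | P(x), p = 0.3 | P(reject given x), p = 0.1 | P(reject given x), p = 0.3 |
|---|---|---|---|---|
| 0 | 0.4783 | 0.0824 | 0.0185 | 0.4304 |
| 1 | 0.3720 | 0.2471 | 0.0896 | 0.6873 |
| 2 | 0.1240 | 0.3177 | 0.3026 | 0.8870 |
| 3 | 0.0230 | 0.2269 | 0.6862 | 0.9802 |
| ≥ 4 | 0.0027 | 0.1260 | 1 | 1 |

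- Type I error: 0.0230 × 0.6862 + 0.0027 = 0.0185.
- Power: 0.2269 × 0.9802 + 0.1260 = 0.348.

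The stated 0.1 and 0.8 are not reproduced. The chance of merely passing stage 1 at p = 0.3 is 0.2269 + 0.1260 = 0.353. No final rule could lift an arm's power above that.

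**Step 2: where the stated figures come from.** The final rule is kept at ≥ 4 of 18 and only the cut is varied.

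| Stop an arm at | Type I error | Power |
|---|---|---|
| ≤ 2 of 7 (as written) | 0.0185 | 0.3484 |
| ≤ 1 of 7 | 0.0560 | 0.6302 |
| 0 of 7 | 0.0893 | 0.8000 |
| no stage-1 stop | 0.0982 | 0.8354 |

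An exact search over two-stage designs for 0.1 against 0.3, with error ≤ 0.1 and power ≥ 0.8, finds a smallest n of 18. Among those designs, the lowest expected size under the null (12.74) belongs to n1 = 7, stop at 0/7, reject at ≥ 4. Section 14.0 matches that design in everything except the stage-1 cut.

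**Step 3: two strata, better one expanded.** All pairs (x, y) from 0 to 7 were enumerated, with the strata independent. The stratum with more responses is expanded if its count exceeds r1, Bin(11, p) is added, and the null is rejected at ≥ 4. Ties are split 50:50 (an assumption). The middle column is rejection in the active stratum; its range covers ties always going against, or always to, that stratum. The per-stratum error is half the any-stratum error, by symmetry.

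| Stage-1 rule | Any rejection, both at 0.1 (per stratum) | Power, one at 0.3 and one at 0.1 (range by tie rule) | Any rejection, both at 0.3 |
|---|---|---|---|
| Section 14.0 as written | 0.037 (0.018) | 0.345 (0.343 to 0.348) | 0.574 |
| Cut at 0/7 | 0.149 (0.075) | 0.715 (0.663 to 0.767) | 0.920 |
| No stop | 0.153 (0.077) | 0.723 (0.663 to 0.784) | 0.922 |

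Under the written cut, selection takes lone-active power only from 0.348 to 0.345, so nearly all the loss is due to the cut. Under a 0/7 cut, selection itself costs 0.800 − 0.715 = 0.085.

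**Step 4: early stopping and enrolment.** Expected enrolment = 14 + 11 × P(continue).

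| Rule | Quantity | Both at 0.1 | One at 0.3 | Both at 0.3 |
|---|---|---|---|---|
| Written cut | P(both strata stop) | 0.949 | 0.630 | 0.419 |
| Written cut | Expected enrolment | 14.6 | 18.1 | 20.4 |
| Cut at 0/7 | P(both strata stop) | 0.229 | 0.039 | 0.007 |
| Cut at 0/7 | Expected enrolment | 22.5 | 24.6 | 24.9 |

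For example, with the written cut and one stratum at 0.3: 14 + 11 × (1 − 0.630) = 18.1. The toxicity stopping rule is not modelled.

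**The case against.** The mismatch in step 1 is not open to dispute. The objections concern the rest.

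- **The natural reading of 0.1 is per arm.** Section 14.0 states its rule arm by arm, and selection can only lower an arm's chance of rejecting. The per-stratum error therefore stays below 0.1 under every reading. This stands: 0.149 and 0.153 exceed 0.1 only if the error is meant for any stratum, which the plan does not say. The misstatement that matters most is power.
- **The cut may simply be miswritten.** Every other parameter fits the 0/7 design, so this is plausible, but the documents do not say so. The printed rule is the operative one, and the chance of missing an active stratum given here is conditional on applying it.
- **Sections 6.1 and 14.0 may not conflict.** Section 6.1 may be a shorter account of the same rule, and section 3.2 calls 25 approximate. This is fair, and the no-stop row is only one possible reading. Even so, a flat total of 25 sits badly with a rule that can stop both strata at 14, and one sentence would settle it.
- **The power figures seem to mix definitions.** They do not. Each is the probability of rejecting in a truly active stratum; with both at 0.3, any rejection qualifies. If one stratum is at 0.3 and rejection in either is counted, the written rule gives 0.360 instead of 0.345.

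**Conclusion.** The concern holds. The figures 0.1 and 0.8 do not describe the design printed in section 14.0. For one arm the exact values are 0.0185 and 0.348, using only the printed rule and no further assumption.

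For the trial as written, with independent strata, ties split evenly and no toxicity stopping, the any-rejection probability is 0.037 under the global null. Power is 0.345 with one active stratum and 0.574 with two. Both strata stop at 14 patients with probability 0.63 when one truly responds at 0.3.

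A 0/7 cut would restore 0.0893 and 0.8000 for a single arm. It would not do so for the selection procedure, where lone-active power is 0.715.

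**What to change.** 1. Reconcile sections 6.1 and 14.0: give one stage-1 cut, say whether it applies to each stratum before the winner is chosen, and say whether 25 is a fixed total or a maximum.
2. Replace the 0.1 and 0.8 sentence with exact figures for the two-stratum procedure, labelled as response-only (toxicity stopping excluded). Define power as rejection in a truly active stratum. Suggested content:
   - Written cut kept: any rejection 0.037 with both strata at 0.1 (0.018 per stratum); power 0.345 if one is at 0.3 and 0.574 if both are; ties split at random.
   - Cut at 0/7: 0.149 (0.075 per stratum); 0.715; 0.920.
   - No stage-1 stop: 0.153 (0.077 per stratum); 0.723; 0.922.
3. State the tie rule and quote the figures that go with it.
4. State whether the primary ORR covers the 18 patients in the selected stratum or all patients.

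The cost is wording and a short calculation, and the quoted figures become less favourable. The maximum stays at 25. If the cut becomes 0/7, expected enrolment rises from 14.6 to 22.5 (both at 0.1), 18.1 to 24.6 (one at 0.3) and 20.4 to 24.9 (both at 0.3).

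The documents do not show whether stage 1 was complete by Version 5.0 (January 2021). If it was, changing the cut is a design change made after data, and the plan must state which rule was actually applied.
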